11. History of interstitial cystitis
12. History of nasal or sinus anomalies or dysfunction e.g. allergic or infectious rhinitis.
13. Patients with lesions to the nasal mucosa
14. Pregnant women, nursing mothers and women of childbearing potential not using contraception known to be highly effective. Highly effective contraception methods include combination of any two of the following:
 - i. Use of oral, injected or implanted hormonal methods of contraception or;
 - ii. Placement of an intrauterine device (IUD) or intrauterine system (IUS);
 - iii. Barrier methods of contraception: condom or occlusive cap (diaphragm or cervical/vault caps) with spermicidal foam/gel/film/cream/ vaginal suppository;
 - iv. Total abstinence;
 - v. Male/female sterilization.
15. Illicit substance abuse within the past 6 months
16. Documented history of medication abuse/misuse (e.g. Unsanctioned dose escalation, broken opioid agreement etc.)
17. Clinical requirement for medications that are concurrent inducers or strong inhibitors of CYP3A4. CYP3A4 substrates are allowed. (Appendix II-D)
18. Porphyria (possibility of triggering a porphyric reaction)
19. Severe active anemia (a hemoglobin< 8 documented by labs drawn within 3 months of first study treatment)
20. History of difficult intravenous access
21. Intractable vomiting

C.10 Informed Consent Process:

Informed consent will be obtained by a research team member delegated to do so by the PI, prior to conducting any research procedures. This process will include a discussion of risks and benefits, as well as answering patient questions. If patients are able to provide their own medical history, they will be deemed capable of providing informed consent for research participation. The process will be free of coercion. Study patients will be paid a small amount to reimburse for travel expenses for each visit completed. They can withdraw at any time without penalty to their ongoing care.

C.11 Compensation for time and effort:

A compensation of \$50 per visit will occur with each patient for each completed visit to reimburse for travel expenses to and from the institution.

C.12 Statistical analysis:

Study results will be analyzed as below to achieve the study objectives:

1. Determine pharmacokinetics of intranasal ketamine.

Concentrations of ketamine and its metabolite norketamine will be analyzed to determine pharmacokinetic characteristics such as bioavailability, peak effect and elimination.

2. Determine pharmacodynamics of intranasal ketamine in terms of Patient Reported Outcomes

- i. Pain scores on NPRS will be analyzed by Wilcoxon signed-rank test as the study sample size is too small to be analyzed by paired t test. Generalized Linear Model will be used to model any time trend for pain score change and to test if the trend is significant.
- ii. T-test will be used to compare any changes in depression severity on MADRS.
- iii. Chi-square test will be used to test presence/absence of any side effects. Wilcoxon signed rank test will be used to assess the severity of all the side effects (including SERSDA), if needed.
- iv. Paired T-test will be used to asses any changes in functional status on PROMIS scale.
- v. T-test will be used to compare any changes in ESAS and ECOG.

3. Determine PK-PD relationships of NAS ketamine delivered

Timing, degree and duration of change in pain scores will be compared with individual and group pharmacokinetic parameters to assess potential relationships between measures of exposure (C_{max} , and AUC_{0-t}) and pain relief. Multivariate modeling including patient-specific data (age, sex, weight, BMI, morphine equivalents) will be performed using initial PK parameters and goodness of fit analyses for compartmental model selection. If applicable, data from vital sign measurement changes will also be used as comparison with pharmacokinetic data.

4. Determine opioid sparing effect of intranasal ketamine.

- i. Chi-square test will be used to compare frequency of rescue medication use.
- ii. T-test will be used to compare total opioid consumption.

C.13 Data and Safety Monitoring and Reporting Plan:

1. This study will be followed by the Winship Cancer Institute Data Safety Monitoring Committee (DSMC) for local review and confirmation of proper study execution and safety measures. Initial study monitoring will occur within 6 months from the date of the first subject accrued, with 2 of the first 5 subjects reviewed. Therefore, subsequent monitoring will occur in six month intervals if any subjects were accrued. The population continuing to receive intervention will be monitored as determined by the DSMC. At minimum, 10% of subjects accrued since previous monitoring will be reviewed. An additional subject (or subjects) may be selected based on previously noted monitoring deficiencies or at DSMC discretion. Continued monitoring will occur in six month intervals for the population continuing to receive intervention as determined by the DSMC.

The DSMC will review pertinent aspects of the study conduct including patient safety, protocol compliance, data collection, and efficacy. The PI or designee will be responsible for notifying the DSMC of patient accrual and status updates within two months of the planned review.

- 2. Procedures to assure data integrity and protocol adherence:**

- a) A monthly meeting of investigators, clinical research coordinators and regulatory personnel will be held to review the clinical data.
- b) Adverse event reporting will utilize the Common Terminology Criteria for Adverse Events (CTCAE) version 5.0. The grading scale for these adverse events is as follows:
Grade 1 Mild; asymptomatic or mild symptoms; clinical or diagnostic observations only; intervention not indicated.

Grade 2 Moderate; minimal, local or noninvasive intervention indicated; limiting age appropriate instrumental activities of daily living (ADL)

Grade 3 Severe or medically significant but not immediately life-threatening; hospitalization or prolongation of hospitalization indicated; disabling; limiting self-care ADL

Grade 4 Life-threatening consequences; urgent intervention indicated

Grade 5 Death related to AE.

c) A serious adverse event (SAE) is an AE or suspected adverse drug reaction that fulfills one of the following:

- results in death
- is immediately life-threatening (life-threatening in the definition of SAE refers to an event in which the subject was at immediate risk of death at the time of the event; it does not refer to an event which hypothetically might have caused death if it were more severe).
- requires in-subject **hospitalization** or prolongation of existing hospitalization
- results in persistent or significant **disability** or incapacity
- is a **congenital anomaly** or birth defect
- is an important medical event: important medical event in the definition of “serious” refers to those events which may not be immediately life-threatening, or result in death, or hospitalization, but from medical and scientific judgment may jeopardize the subject and/or may require medical or surgical intervention to prevent one of the other outcome listed above. Examples of such events are intensive treatment in an emergency room or at home for allergic bronchospasm, blood dyscrasias or convulsions that do not result in hospitalization. Development of cancer or drug dependency or drug abuse will normally be considered serious by this criterion.

d) Study progress in terms of enrollment and activity of current patients will be reviewed during the monthly meeting of the investigators, clinical research coordinators and regulatory personnel. The PI may increase the frequency of this meeting if necessary.

e) Study specific training of all study personnel, including management of potential adverse events, will occur prior to initiating study enrollment using the final approved protocol and study specific standard operating procedure document. Training of the Phase I staff will be conducted by the team clinical research coordinator prior to study enrollment. Completion of training will be documented on a study training log and stored in the regulatory binder. Investigators will complete CITI training as well as any additional training required by the Emory Office for Clinical Research.

3. Clinical monitoring will occur as previously described (Study Methods).
4. As the IND sponsor-investigator, unexpected fatal or life threatening suspected adverse reactions will be reported using the Medwatch FDA form 3500A via FedEx to the FDA no later than 7 calendar days after the initial receipt of information (21CFR 312.32(C)(2)). Additionally, serious, unexpected suspected adverse reactions and a clinically important increase in the rate of a serious suspected adverse reaction will be reported to no later than 15 calendar days after determining the information qualifies for reporting (21 CFR 312.32 (C) (1)) in paper format using FDA form 3500A. Finally, an annual progress report will be provided within 60 days of the anniversary date that the IND became active , January 20, 2017, (21 CFR 312.33).
5. Patient data will be evaluated by the PI on an ongoing basis during the study visits to observe for any trends in adverse effects of the study treatment, to ensure continued subject safety and to ensure the scientific validity of the trial. Adverse events (AE) will be recorded. An adverse event is defined as any untoward medical occurrence in a patient or clinical investigation subject administered a pharmaceutical product or study treatment and that does not necessarily have a causal relationship with this administration. An AE can therefore be any unfavorable and unintended sign (including any abnormal laboratory findings), symptom, or disease temporally associated with the use of a medicinal (investigational) product, whether or not related to the medicinal (investigational) product. Adverse events will be captured from the time of the first study drug administration through the fifth study visit. Ongoing adverse events at the fifth visit will be followed with a telephone call visit 14 days (plus or minus 1 day) after the last medication administration. AEs will be reported to the PI by Emory email or telephone. All adverse events will be documented in an AE log. The reporting policy of the Emory IRB will be followed.
6. The study will be stopped after a hospitalization that is related to study drug administration for a formal review by the PI and the DSMC. When a hospitalization related to study drug administration occurs, the study will be put on hold. The PI or delegated person will communicate the event details to the DSMC for their review and determination of approval to continue the study. The study will be ended if there is more than one hospitalization related to the study drug administration.
7. The Emory University School of Medicine Department of Anesthesiology will conduct this study according to national rules, regulations and guidelines governing human clinical research. In addition,

procedures cited by the US Code of Federal Regulations (Title 21) will be followed as these apply to the principles of Good Clinical Practice and approval by the Emory University Institutional Review Board (IRB).

Confidentiality: The privacy of the research subjects will be ensured through the standard procedures for securing research data. All records identifying the subject will be kept confidential and, to the extent permitted by the applicable laws and regulations, will not be made publicly available. Subjects will be identified by a study number. If the results of the study are published, the subject's identity will remain confidential.

C.14 Potential Pitfalls:

Lack of blinding/Lack of placebo arm. There is enough evidence to support an analgesic effect of ketamine. Since the study is being conducted in cancer pain patients and involves blood draws and transport, a placebo arm is considered to be unethical in these circumstances. The possibility exists that **ketamine might have long term effects beyond its duration of action** and the pain scores might be significantly lower than the compared to at the beginning of the study. In this case **change in pain score may not be significant during the later study visits**. However, overall this would be a good effect for pain control and can future studies can be designed to account for this effect. As cancer pain can be evolving and changing, the decision was made to finish all the study visits in the least possible duration of time, as possible. Once feasibility and safety is established with this study, the aim of future studies will be allow patients to take this medication at home for maintenance. **Lack of standard opioid regimen** among patients could be problematic in terms of comparison of outcomes.

E. REFERENCES/BIBLIOGRAPHY

1. van den Beuken-van Everdingen, M. H. *et al.* Prevalence of pain in patients with cancer: a systematic review of the past 40 years. *Ann Oncol* **18**, 1437-1449, doi:10.1093/annonc/mdm056 (2007).
2. Malinovsky. Ketamine and norketamine plasma concentrations after i.v., nasal and rectal administration in children. *Br J Anaesth* , 77(72):203-207 (1996 Aug;).

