Ketamine has a rapid onset and relatively short duration when administered as a single intravenous dose. Onset of action for intravenous dose is 30 seconds; distribution half-life 10 minutes; elimination half-life 2-3 hours. Oral bioavailability is poor (20-25%) possibly due to the hepatic first pass effect/GI tract effect. Ketamine undergoes rapid demethylation to norketamine via cytochrome P450 (CYP) conversion, with CYP3A4 being the principle pathway, with minor and clinically insignificant contributions from CYP2B6 and CYP2C9.⁵⁰ Bioavailability of intranasal ketamine was found to be 50% in children aged 2-9 year old in a study done by Malinkovsky et al. in 1996². However this study was done in children and the subjects did not serve as their own controls. In a study by Yanagihara et al. in 2002 the bioavailability of intranasal ketamine was found to be 45%. In this study the subjects served as their own controls, however, the number of subjects was limited to 3. The time for maximum concentration after *intranasal* ketamine administration was found to be 22.5(+ 9.6) min for ketamine and 120(+ 52) min for its metabolite norketamine. The $T_{1/2}$ _{β} (elimination half-life) of *IV* ketamine is reported to be 126.8(+47.4) min by Yanagihara et al²³. Elimination half-life of intranasal ketamine has not been reported. Ketamine has high lipid solubility and crosses the blood-brain barrier quickly, and exhibits high hepatic clearance and a large volume of distribution. It undergoes extensive hepatic metabolism by the cytochrome P-450 system to form the

active metabolite, norketamine. Norketamine is one-third to one-fifth as potent as Ketamine. Norketamine is eventually conjugated to form more inactive metabolites that are excreted by the kidneys.

A3. Preliminary Data:

To date, we have collected data on two cases of cancer patients to whom ketamine was delivered palliatively for pain unresponsive to usual interventions:

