Although ketamine has been used as an adjunct to opioid medication for pain, there is no data on intranasal ketamine for cancer-related pain. If studied extensively, this could potentially provide physicians with a simple option and unique adjunct to treat pain. Ketamine could also modulate central sensitization and hyperalgesia which are some of the mechanisms involved in development of chronic pain. This could potentially help decrease the severity of pain in general. Depression often coexists with cancer, and intranasal ketamine has the potential to improve depressive symptoms when used chronically.

Intravenous ketamine is used by pain physicians to control pain not responding to opioid medications in the hospital setting. However, it is not continued as an outpatient therapy as absorption of oral ketamine is limited to 25%. Intranasal ketamine, if feasible, will provide clinicians with an option to continue ketamine chronically. There is also lack of long term studies regarding use of ketamine for pain. Future long term studies with intranasal ketamine for pain control can be designed based on data obtained from the current proposed study.

The route of administration can be limited in terminally ill patients as many suffer from nausea and vomiting (limiting the oral route) and have dehydration making it difficult to find veins for intravenous route. A study, focusing on the effects of chemotherapy on Chemotherapy Induced Nausea Vomiting (CINV), and the effect of CINV on daily life found that 36% of all patients reported emesis and 60% reported nausea. Intranasal route is underutilized for medication administration, especially pain medications in cancer patients. If successful, this study will open new horizons of medication delivery and pain control in this population.

Objectives

Overall Goal: To determine the safety, feasibility, and utility of intranasal (NAS) ketamine in persistent uncontrolled cancer related pain.

Specific Aims:**Primary Outcomes****1. To conduct a clinical trial of NAS ketamine in a sample of patients with cancer related pain.**

1a. To measure pharmacokinetics of NAS ketamine through analysis of ketamine and its metabolite norketamine to determine pharmacokinetic variables including peak concentration after each dose and route (C_{max}), time to peak concentration (t_{max}), total area under-the-concentration-time curve (AUC_{0-t}), half-life ($t_{1/2}$), and clearance (Cl).

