intranasal doses of ketamine at 10 mg, 30 mg and 50 mg ²⁸. Therefore, for study purposes 10mg, 30 mg and 50mg of intranasal ketamine will be administered. Each visit will be two to seven days apart to avoid any accumulation of study doses. Subjects will be recruited at the supportive oncology clinic, oncology clinics, the pain clinic and Acute Pain Service at Emory. Subjects may be identified and contacted via telephone with information about the study prior to their next clinic appointment in order to allow time for them to consider the study. After informed consent has been obtained, study eligibility will be confirmed (see Table of Assessments). An appointment will be made for the Phase I Unit at Winship. A family member/friend must transport the patient home following drug administration, as driving for 24 hours post drug administration is discouraged. Written informed consent will be obtained prior to performance of study procedures, either while recruiting prior to study visit one or during the first study visit, prior to beginning the study. Subjects must meet all study eligibility criteria on Visit 1 prior to study treatment. Patients will be asked to return to the Phase 1 Unit for a total of 5 study visits. All study visits to the clinic will take place within six weeks or less. A telephone call visit will occur 14 days after the last dose of medication administered to follow any ongoing adverse events that occurred during the study period. If there are no ongoing adverse events at the end of visit five, the subject's participation will end at that time. Subjects may be reconsented if withdrawn early, at the discretion of the investigator, provided all eligibility requirements are met.

Table of Assessments

Assessments	Screening	Visit One	Visit Two	Visit Three	Visit Four	Visit Five	Telephone Call
Review of Inclusion/Exclusion	X						
Informed Consent	X						
Med Hx/Demographics	X						
Hemoglobin (if none within 3 months of Visit One)		X					
Urine pregnancy test-within one week of planned Visit (women of child bearing potential)		X	X	X	X	X	
PHQ9 Depression Screening	X	X ¹					
Completion of PROMIS Questionnaire		X				X	
ECOG score		X	X	X	X	X	
ESAS		X	X	X	X	X	
MADRS ^{2,3}		X	X	X	X	X	
Height		X					
Weight		X	X	X	X	X	
IV access		X	X ⁴	X	X		
Study Medication Administration		X	X	X	X		
Vital Signs(HR ⁵ , BP, RR, Pulse Oximetry ⁶)		X ⁷	X ⁷	X ⁷	X ⁷	X ⁸	
Blood Samples (PK)		X ⁹	X ^{9,10}	X ^{9,10}	X ^{9,10}	X ¹⁰	
Hepatic Function test		X				X	

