Dose Finding. Escalating dosages of intranasal ketamine will be given during the study in order to find optimal analgesic dose without significant side effects. On the first study visit, after obtaining written informed consent, 10mg of intranasal ketamine will be given to make sure that the study patients are able to tolerate a small dose of NAS ketamine. On the second visit, 10 mg of IV ketamine will be given to help establish bioavailability of NAS ketamine, with patients serving as their own controls. On the third and fourth visit, higher doses of ketamine, 30 mg and 50 mg respectively, will be given, if the patients did not have severe adverse events with the smaller dosage. Licensed study personnel delegated to do so, will administer ketamine. The intranasal ketamine will be administered as follows: 1) Ensure mucosal atomization device (MAD) is primed and the appropriate dose loaded into the syringe. 2) Have patient sit in chair and clear sinuses using a tissue if needed. 3) Tilt the patient's head back. 4) Insert MAD into nostril and aim directly posterior, level with the floor of the nare, and slightly lateral. 5) Administer 0.1mL (10mg). 6) Have patient keep his head tilted back for 5 minutes, if tolerable, to ensure that the medication does not run out of nares. Make a note if medication is visibly noted to run out of nares or if patient reports feeling of medication trickling down his throat. 7) If more than 0.1mL (10mg) needs to be delivered, repeat steps 3-5 in the contralateral nare, alternating until the full dose is delivered. Ensure 30 seconds have passed before re-administration into the same nare. Patients may continue to take their usual pain medication as needed. Since most of the oral immediate release opioid medications peak between 30 to 90 minutes, ketamine will be given at least 120 minutes after the last dose of immediate release opioid medication so the reduction in pain score is not confounded with the results of immediate release opioid medications. Pain scores will be recorded on NPRS prior to and at 5, 10, 15, 30, 45, 60, 120, and 180 and 240 minutes after administration of test medication. NPRS is the most responsive tool to document pain intensity when compared to Visual Analogue Scale (VAS) and Visual Rating Scale (VRS) for measuring pain,²⁹ showing higher compliance rates, better responsiveness, ease of use, and good applicability relative to VAS/VRS³⁰. In general, improvements of pain severity</=1.5 points on NPRS could be seen as clinically irrelevant³¹⁻³⁴. Above that value, the cutoff point for "clinical relevance" depends on patients' baseline pain severity, and ranges from 2.4 to 5.3³³⁻³⁵. Higher baseline scores require larger raw changes to represent clinically important differences³⁶.

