
Concomitant Opioid medications: As the study subjects will have uncontrolled pain it is likely that they might be on opioid medications during the study. Georgia prescription monitoring database will be searched by the investigators and an opioid pill count will be done at each visit to monitor opioid intake during the study.

Pharmacokinetics. Blood samples will be drawn at 2, 30, 60 and 240 minutes. Baseline blood samples will be drawn on visits 2 through 5. The specimen requirements for lab testing are 3 ml serum or plasma in EDTA containing vacuum tubes. We will draw 6 ml of blood per sample to allow for adequate serum/plasma sample. The total blood drawn during one visit would be 24 to 30 mL. Samples will be promptly centrifuged and serum or plasma will be separated into a plastic cryovial and frozen. The plastic containers will be preservative free. All samples will be sent within 3 months to National Medical Services. The samples are valid for 7 months at -20°C, 30 days when refrigerated or stored at room temperature. Samples will be destroyed immediately after analysis. A gas chromatography with mass spectrometry (GC/MS) analysis of the samples will be done for concentrations of ketamine and its metabolite, norketamine. Plasma concentration-time curves for ketamine and norketamine will be generated for each subject and compared within subjects for the variables of route and dose, with IV administration serving as the basis for comparison.

Additional Labs: Liver function test (LFT) and urinalysis (UA) will be done on visits 1 and 5.

Patient Reported Outcomes. Patients will maintain a pain diary(Appendix I-J) for the entire study period up until the 5th and final study visit and record how often they took their usual breakthrough medication during the trial.

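### No PK draw lies between 60 and 240 min, although the protocol cites a nasal norketamine tmax of 120 min, so norketamine Cmax and tmax (and, less so, AUC) would be poorly observed

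*Combined protocol and SAP*

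**What the plan says.** C.2 Methods, Pharmacokinetics: "Blood samples will be drawn at 2, 30, 60 and 240 minutes". Footnote 9 of the Table of Assessments gives the same times for visits 1 to 4, with windows of 5 min at 30 and 60 min and 15 min at 240 min. Footnote 10 adds baseline draws on visits 2 to 5.

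Section A2 gives the time of maximum concentration after nasal dosing as "22.5(+ 9.6) min for ketamine and 120(+ 52) min for its metabolite norketamine". It does not say whether the bracketed figures are SDs or SEs. The adult study described just before is noted as small: "however, the number of subjects was limited to 3". It may be the source.

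Specific Aim 1a, under Primary Outcomes, rests on "analysis of ketamine and its metabolite norketamine to determine pharmacokinetic variables including peak concentration", and goes on to tmax, AUC0-t, half-life and clearance. The Pharmacokinetics paragraph adds: "Plasma concentration-time curves for ketamine and norketamine will be generated for each subject".

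C.12 item 1 gives no estimation method. Compartmental model selection appears only in C.12 item 3, on PK-PD relationships, and no norketamine structure is named.

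**The concern.** The protocol's only figure for the metabolite peak lies in a three-hour stretch without a sample. One SD either side of it (68 to 172 min) stays inside the gap even with the sampling windows, which leave 65 to 225 min uncovered.

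If Cmax and tmax are taken from the samples, the metabolite peak will be recorded too low and at the wrong time. If they are fitted, each visit has one point after 60 min, so a poorly chosen model would be hard to detect. Norketamine is the active metabolite, and the results are meant to inform a later trial.

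**Working it through.** **1. The schedule against the stated blood volume.** Each sample is 6 mL. Visit 1 has 4 draws: 4 × 6 = 24 mL. Visits 2 to 4 have 5 draws: 5 × 6 = 30 mL. This reproduces the stated 24 to 30 mL per visit, so no further draw is implied.

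**2. Share of norketamine peaks between 60 and 240 min.** Inputs are the cited mean 120 and the bracketed 52.

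| Reading of 52 | Distribution of tmax | Share in gap |
|---|---|---|
| SD | Normal(120, 52) | 86.5% |
| SD | lognormal, same mean and SD | 89.8% |
| SD from 3 subjects, predictive | 120 + 52·√(4/3)·t(2 df) | 69.7% |
| SE from 3 subjects | Normal(120, 52·√3 = 90.1) | 65.6% |

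**3. Observed norketamine values.** Curve: C(t) ∝ exp(−ke·t) − exp(−kf·t), with tmax = ln(kf/ke)/(kf − ke). The norketamine half-life is not in the documents; 1.5, 3, 5 and 7 h are assumed. The formation rate kf is solved for tmax of 68, 90, 120, 150 and 172 min. AUC0-240 is by linear trapezoid.

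Example, half-life 180 min and tmax 120 min. Then ke = ln2/180 and kf = ln2/45, and ln(4)/(0.01540 − 0.00385) = 120.
- C at 2, 30, 60, 120 and 240 min: 0.0227, 0.2609, 0.3969, 0.4725, 0.3721.
- Planned draws: the highest sample is at 60 min, and 0.3969/0.4725 = 84% of true Cmax.
- Planned AUC: 0.02 + 3.97 + 9.87 + 69.21 = 83.07. True AUC is 93.32. Ratio 0.89, or 11% low.
- With draws at 15, 30, 60, 120 and 240 min (C at 15 min is 0.1502): 1.13 + 3.08 + 9.87 + 26.08 + 50.68 = 90.84. Ratio 0.97, and observed Cmax is exact.

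Over the whole grid:

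| | Planned | With 15 and 120 min |
|---|---|---|
| tmax 120: Cmax, % of true | 82-88 | 100 (by construction) |
| tmax 120: AUC0-240 | 8-13% low | 2-3% low |
| tmax 68-172: Cmax, % of true | at least 82 | at least 94 |
| tmax 68-172: AUC0-240 | 3-13% low | 0.5-3.4% low |
| tmax 68-172: recorded tmax | 60 or 240 | 60, 120 or 240 |

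Linear-up/log-down AUC on the same curves leaves the planned range at 3-13% low and gives 1.1-3.6% low after the change.

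**4. If values are fitted with the right model.** Assumptions: one-compartment form, half-life 4 h, 10% error, 20% between-visit variability, one fit per patient over three nasal visits. Fitted tmax is within 30 min of truth in 100/98/90% at tmax 90/120/150 as planned, and 100/100/90% with the added draws. Median Cmax is about 1.00 of true. Half-life stays poor: the 5th to 95th percentile is 1.4-11.1 h as planned and 1.4-10.8 h afterwards, against a true 4 h.

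**5. Ketamine bioavailability ratio.** IV curve: A·exp(−αt) + B·exp(−βt), with half-lives of 10 min (cited) and 127, 153 or 180 min (within or near the cited range), and A/B of 1, 3 or 10 (assumed). Nasal absorption is first order, solved for tmax 12.9, 22.5 or 32.1 min (22.5 ± 9.6). That gives 27 scenarios. IV concentration at time 0 is back-extrapolated. The sampled nasal/IV AUC0-240 ratio is divided by the true one.

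| Schedule and AUC rule | tmax 12.9 | 22.5 | 32.1 |
|---|---|---|---|
| Planned, log-down | 0.86-0.93 | 0.94-0.98 | 0.93-0.96 |
| Package, log-down | 0.91-0.96 | 0.95-0.97 | 0.95-0.97 |

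Under linear AUC the planned ratio is 0.83-0.93 at tmax 12.9 and 0.90-0.96 at 32.1. Adding only the 120-min draw with linear AUC gives 0.77-0.95 across the scenarios. The full set of new draws with linear AUC still gives only 0.85-0.97.

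**The case against.** Several points on the other side have force.

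- **Modelling may close the gap.** A reader might infer that norketamine Cmax, tmax and AUC are planned to rest on an unnamed model. The documents do not say so: C.12 item 1 gives no method, and the compartmental wording belongs to PK-PD. If a correct model is fitted, the gap costs little (step 4). This stands, so the firm finding is about observed values.
- **A second, swallowed input.** A reader might infer that the protocol expects part of the nasal dose to be swallowed, which would defeat a single-input model. Dose Finding only asks staff to make a note "if patient reports feeling of medication trickling down his throat". It gives no expectation, fraction or timing. Any such scenario is an assumption of this review, and no size is claimed from it.
- **The reference tmax is weak.** It may come from 3 subjects. That widens the share to 66-90%, but a majority of peaks falls in the gap under every reading.
- **Importance.** The study seeks preliminary data in 10 completers, Aim 1a is about nasal ketamine, and the protocol puts norketamine at one-third to one-fifth of ketamine's potency. If tmax is similar across doses, much of the bias cancels between nasal visits. This lowers the severity. It does not help the absolute values, and cancellation against the IV visit cannot be assumed.
- **A 120-min draw alone can do harm.** This is correct for the ketamine ratio with linear AUC, which is why the fix is a package.

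**Conclusion.** The concern holds for observed norketamine values. About 66-90% of metabolite peaks fall where nothing is sampled, and those patients would be recorded at 60 or 240 min. At a true tmax of 120 min, Cmax is 82-88% of true and AUC0-240 is 8-13% low. Over tmax 68-172 min AUC is 3-13% low, so AUC suffers less than Cmax and tmax. These sizes assume a one-compartment norketamine curve and a half-life of 1.5-7 h, neither of which the documents give.

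A reader might also infer that ketamine bioavailability is undermined. The figures do not support that: at the cited mean tmax the planned ratio is 0.94-0.98 of true, and the loss is mainly in patients who peak early.

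Severity is minor to moderate: a cheap improvement to a listed aim.

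**What to change.** Make these changes together:

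1. Add a 120-min draw on visits 1 to 4, keeping 30, 60 and 240 min.
2. On nasal visits (1, 3 and 4) move the 2-min draw to 15 min, and pre-specify linear-up/log-down AUC. The ketamine ratio is then 0.91-0.97 over tmax 12.9-32.1 min, against 0.86-0.98 as planned under the same rule.
3. State whether norketamine values are observed or fitted, and report observed Cmax and tmax beside any fitted ones. Label norketamine half-life exploratory, since sampling still ends at 240 min.

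**Cost.** A protocol amendment to the sampling times. Draws per completer rise from 20 (16 post-dose and 4 baseline, 120 mL) to 24 (144 mL, +24 mL or 20%), which is 40 more assays for 10 completers. Blood per dosing visit becomes 30 to 36 mL. Extra blood matters, since C.9 item 19 excludes only hemoglobin below 8.

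**Volume-neutral option.** Drop the baseline draws on visits 2 to 5. The total stays at 20 draws and 120 mL, with at most 5 × 6 = 30 mL per visit. This loses a carry-over check, but one of little value given the spacing: "Each visit will be two to seven days apart to avoid any accumulation of study doses". At 48 h and a 3 h ketamine half-life, 16 half-lives leave 0.0015%. At an assumed 7 h for norketamine, 48/7 = 6.9 half-lives leave 0.86%.

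The nasal 2-min point is lost either way. The new times fit existing on-site assessments with IV access in place: "Pain scores will be recorded on NPRS prior to and at 5, 10, 15, 30, 45, 60, 120, and 180 and 240 minutes".

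If sampling cannot change, label norketamine Cmax, tmax and half-life exploratory.
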